### 2. Treatment index

#### **Primary Objective -- New users of DEX (DEX+) versus matched non-users of CSI (CSI-):**

From the patients who enter the cohort, new users of DEX between the admission date (*Day 0*) and 1 day prior to discharge date (*Day D-1*) or a maximum period of 21 days after admission (*Day 21*) will be selected. Greater than 80% of the patients who initiated DEX did so within 1 or 2 days of their hospitalization. A sensitivity analysis (SA2) will be conducted to explore initiation dates further. For each new user of DEX, at least 1 patient who has not (yet) used any CSI as of the DEX patient's index date or within the 90-day washout period prior matched on the

criteria defined in Table 2 below will be randomly risk-set sampled (RSS). DEX+ versus CSI-matching ratios of 1:1, 1:2, 1:3, and 1:4 will be considered to select up to 4 non-user referent patients for each exposed, and the ideal ratio will be selected based on the diagnostic criteria [defined below in section *VI.B. Diagnostic phase and checklist*].

RSS matching allows us to proxy the ‘standard of care’ by randomly selecting 1 or more patients who have not initiated DEX from the risk set of patients who are eligible for initiating DEX at the same time [*Li 2001*]. Since the COVID-19 pandemic and treatment of patients with COVID-19 is rapidly changing over time, there is much potential for calendar-time bias. Furthermore, patients prescribed DEX may appreciably differ from those not prescribed DEX. Employing an RSS that matches DEX users and non-users on the date of DEX treatment (in the users) and time since admission will minimize the potential for this bias. Cohort entry month will also be included in the propensity score (PS) calculation to further adjust for time-related biases. Geographic region was considered for the RSS matching criteria. However, during our data explorations, the comparison of baseline balance showed that matching without region yielded better baseline balance than matching with region. Therefore, we removed region from the RSS matching. However, given known regional differences, we still account for region in our propensity score model.

The *treatment index date* (Day T) for patients who are users and for the matched non-user referent patients will be defined by the index date of the matched users.

### **Secondary Objective I -- New users of DEX (DEX+) versus matched non-users of DEX (DEX-):**

From the patients who enter the cohort, new users of DEX between the admission date (*Day 0*) and 1 day prior to discharge date (*Day D-1*) or a maximum period of 21 days after admission (*Day 21*) will be selected. For each new user of DEX, at least 1 patient who has not (yet) used DEX as of the DEX patient's index date or within the 90-day washout period prior matched on the criteria defined in Table 2 below will be randomly RSS. DEX+ versus DEX- matching ratios of 1:1, 1:2, 1:3, and 1:4 will be considered to select up to 4 non-user referent patients for each exposed, and the ideal ratio will be selected based on the diagnostic criteria [defined below in section *VI.B. Diagnostic phase and checklist*].

### **Secondary Objective II -- New users of DEX (DEX+) versus new users of MPRED (MPRED):**

From the patients who enter the cohort, all patients who begin use of DEX or MPRED between the admission date (*Day 0*) and 1 day prior to discharge date (*Day D-1*) or a maximum period of 21 days after admission (*Day 21*). New use will be determined using a 90-day washout period to exclude patients with prior use of either DEX or MPRED during the 90 days prior. If a patient uses both treatments over the course of the admission, they will be assigned to their first qualifying treatment arm. If a patient receives both DEX and MPRED on the treatment index, they will be excluded since the effects or the drugs cannot be disentangled among these patients.

*Table 2: Risk set sampling (RSS) matching criteria*

RSS matching criteria	Variable type	Categories (for categorical) / calipers (for continuous)
Calendar date	continuous	±3 days
Age	continuous	±3 years
Sex	categorical	male, female
Combined comorbidity score over 183d baseline period [ Gagne 2011 ]	categorical	0-1, 2-3, 4-5, 6+
Time since hospital admission	categorical	0-1, 2-3, 4-5, 6 - 9, 10 - 14, 15 - 19, 20+ days
COVID-19 severity at treatment index date, per modified WHO (mWHO) score	categorical	No O2, O2/NIV, IMV (highest recorded from days T-1 to T) [see additional subgroup detail below in section V.D. Subgroups ]

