### III. RESEARCH AIM AND OBJECTIVES

As part of the RCA with the FDA, this study informs the overall project to establish a system for rapid-cycle evaluation, using best practice scientific and operational methods, as applied to relevant and meaningful clinical questions. In this study, we seek to assess the effectiveness of DEX to reduce the risk of inpatient mortality within 28 days among US patients hospitalized with COVID-19 diagnosis or SARS-CoV-2 infection, overall and stratified by COVID-19 severity subgroups [defined according to the presence of encounters indicating supplemental oxygen or ventilation; see *section V.D* for additional subgroup detail], using the HealthVerity database.

The principles outlined by Hernan et al. emphasize the importance of explicitly emulating a hypothetical target trial when planning a RWD analysis to yield RWE [Hernan, Robins 2016; Hernan, Sauer 2016]. Although we reference the UK RECOVERY trial as a basis for comparison [RECOVERY 2020], we sought to emulate a hypothetical target trial with varied design elements, and research questions tailored for US practice and US patients. In a sensitivity analysis, we further sought to replicate the RECOVERY trial design elements (to the extent possible) [see *section VII. Sensitivity Analyses, SA8*].

Specifically, among US patients hospitalized with COVID-19 diagnosis or SARS-CoV-2 infection without prior use of any corticosteroid of interest (CSI; DEX, methylprednisolone, prednisone, hydrocortisone) estimate the hazard ratio and corresponding 95% confidence interval for the risk of inpatient mortality within 28 days after treatment initiation, comparing *new use of DEX* with:

- *non-users of corticosteroids (Primary objective I; DEX+ vs. CSI-)*, to evaluate the potential benefit of DEX above ‘standard of care’ inpatient treatment for COVID-19, where ‘standard of care’ excludes all CSIs (DEX, MPRED, PRED, HC).
- *non-users of DEX (Secondary objective I; DEX+ vs. DEX-)*, to evaluate the potential benefit of DEX above ‘standard of care’ inpatient treatment for COVID-19, where ‘standard of care’ excludes DEX but may include those newly treated with a non-DEX CSI (MPRED, PRED, HC). This comparison is most similar to the RECOVERY trial that compared DEX to ‘standard of care’ [RECOVERY 2020].

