- *methylprednisolone active comparator (Secondary objective II; DEX+ vs. MPRED+)*, to evaluate the potential benefit of DEX compared to a clinically meaningful treatment alternative (here, another corticosteroid), among patients without prior use of DEX or MPRED (traditional new user design). This comparison excludes those treated with a CSI other than DEX and MPRED.

Under the assumption that all of the CSIs are protective [NIH 2020(c)], we would expect a stronger effect for CSI- comparison (**Primary objective**), some protective effect for the DEX- comparison (**Secondary objective I**), and little or no effect for the MPRED+ comparison (**Secondary objective II**).

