### A. Study design

This study is an observational cohort study using secondary healthcare data. The study diagram and its components are illustrated and further detailed below [*see Figure 2*].

Figure 2. Study diagram

Inclusion/Exclusion Criteria	
COVID-19 confirmation	Hospitalized patients with confirmed COVID-19 (ICD 10 diagnosis: U07.1 or positive or presumptive positive SARS-CoV-2 diagnostic laboratory test result; Day -21 to Day T).
Baseline Exclusion	Exclude patients without activity in the 183 day baseline period (Day -183 to Day -1).
Missing Demographics Exclusion	Exclude patients with missing age, sex, or region on the hospital admission date (Day 0; CED).
COVID-19 Vaccine Exclusion	Exclude patients with any record of a COVID-19 vaccine on or any time prior to the treatment index date given that these patients are assumed to be selectively different (Day S to Day -1).
Treatment Exposure	Hospitalized COVID-19 patients with new use of systemic dexamethasone (DEX+) or referent groups (CSI-, DEX-, MPRED+). Treatment index date (Day T) must occur between hospital admission date (Day 0; CED) and 1 day prior to hospital discharge date (Day D-1).
Treatment Washout	Exclude patients with prior systemic CSI use from all comparisons (Day -90 to Day T-1).
Covariate Assessment	
Baseline	Baseline (pre-admission) comorbidities, co-medications, and healthcare resource utilization (HCRU; Day -183 to Day -1).
Pre-admission	COVID-19-related symptoms, complications, and HCRU leading up to the hospital admission date (Day -21 to Day -1).
On admission	Demographics, facility characteristics, and covariates related to admitting status (Day 0; CED).
Pre-treatment (Inclusive)	Treatments administered prior to or concurrent with treatment index date, pre-treatment clinical status, and time from admission to treatment (Day 0 to Day T).
mWHO Severity	COVID-19 severity per modified version of WHO ordinal scale (mWHO), used for matching and subgrouping of DEX+ and referent patients (Day T-1 to Day T).
Outcome Assessment	
Follow-up	Follow-up window for primary outcome of 28-day inpatient mortality (Day T+1 to the earlier of Day T+28 or D).

*CED, Cohort Entry Date; D, Hospital discharge date; S, Start of available data; T, Treatment index date*

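### The primary comparison's rules leave patients who start DEX and another systemic corticosteroid on the same Day T in the DEX+ arm, while its referents must be free of any corticosteroid through Day T

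*Protocol*

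**What the plan says.** Section III (Research aim and objectives) frames the primary objective as "to evaluate the potential benefit of DEX above" a standard of care that contains none of the four CSIs: DEX, methylprednisolone (MPRED), prednisone (PRED) and hydrocortisone (HC).

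Section V.C.2 (Treatment index) builds the two primary arms differently on Day T. The exposed arm is drawn from all "new users of DEX between the admission date" and the day before discharge, up to Day 21, with no condition on other CSIs given that day. Each DEX user is then matched to "at least 1 patient who has not (yet) used any CSI as of the DEX patient's index date".

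The washout in the Figure 2 table of section V.A reads "Exclude patients with prior systemic CSI use from all comparisons (Day -90 to Day T-1". The exclusion list in V.C.3 also ends at T-1. Section V.B defines new use by the absence of earlier systemic DEX and does not mention other CSIs.

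Secondary Objective II is stricter. Of patients given both DEX and MPRED on the index date, V.C.2 states that "they will be excluded since the effects or the drugs cannot be disentangled among these patients", and section III adds "This comparison excludes those treated with a CSI other than DEX and MPRED".

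**The concern.** The protocol recognises that two corticosteroids started together cannot be credited to one of them, and acts on this only in a secondary comparison. In the primary comparison the Day T condition binds one arm. A referent who takes any CSI on Day T is ineligible, while a DEX starter who takes another CSI on the same day stays in.

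Two things are at stake. First, what the primary hazard ratio describes: section III credits it to DEX, but the arm as built is DEX with or without another CSI at index. Second, comparability across objectives: section III predicts a stronger effect against CSI- than against MPRED+, yet the DEX+ arm keeps same-day co-starters in the first comparison and drops them in the second. Part of any difference between the two results could therefore reflect who is in the DEX+ arm.

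**Working it through.** The protocol gives no count of same-day co-starters and no hazard ratio for them, so there is no figure to reproduce. The check is a reading of the rules side by side, followed by an illustration on stated assumptions.

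**Step 1. Is another CSI on Day T caught by any rule?**

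| Rule (section) | Primary DEX+ | Primary CSI- | Secondary II |
|---|---|---|---|
| CSI washout (V.A, V.C.3) | ends T-1, not caught | ends T-1 | ends T-1 |
| New-use definition (V.B) | prior DEX only, not caught | not applicable | prior DEX only (V.B); prior DEX or MPRED (V.C.2) |
| Arm selection (V.C.2) | every new DEX user, not caught | no CSI as of index, caught | DEX and MPRED together on Day T excluded |
| Other CSIs (III) | no rule | barred | PRED and HC excluded |

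All windows are in whole days, so a patient given another CSI first and DEX later on the same day is also DEX+.

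**Step 2. Does anything later in the plan repair it?**

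- Covariates (V.F, Table 3): the co-medications counted through Day T are anticoagulants and antiplatelets, antibiotics, and other listed COVID-19 therapies. No systemic corticosteroid is named. The steroid covariate is in the baseline window, Day -183 to Day -1.
- Propensity score matching (VI.A) cannot balance a characteristic that the CSI- arm is defined not to have.
- As-treated censoring (V.E), for the primary objective, acts only on CSI- patients.
- SA1 to SA8 (VII): none removes same-day co-starters. SA8 drops the washout and so admits more prior use.

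**Step 3. How far could the estimate move?** Let f be the share of DEX+ patients with another CSI on Day T, and HRc their hazard ratio against CSI-. Take 0.80, the planning value in Table 4, for DEX alone. As a rough average:

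observed HR ≈ (1 − f) × 0.80 + f × HRc

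Both f and HRc are assumptions.

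| f | HRc = 0.6 | HRc = 1.0 | HRc = 1.5 |
|---|---|---|---|
| 1% | 0.798 | 0.802 | 0.807 |
| 5% | 0.790 | 0.810 | 0.835 |
| 10% | 0.780 | 0.820 | 0.870 |

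Example: 0.90 × 0.80 + 0.10 × 1.5 = 0.72 + 0.15 = 0.87. The shift is negligible at 1% and visible at 10%, and its sign depends wholly on HRc.

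**The case against.** The best defence is that the two rules serve different purposes. In Secondary II both drugs define arms, so a same-day user of both belongs to both arms and cannot be assigned. In the primary comparison that patient is plainly a DEX initiator and cannot be CSI-. Section V.B defines exposure as starting systemic DEX, not as DEX alone, and a study of routine use may reasonably keep such patients. This stands in part: the two rules do not contradict each other. But the reason the protocol gives is that the effects cannot be separated, not that the arm is ambiguous, and that reason applies equally to the primary comparison. Nor does the protocol say that DEX with or without another CSI is the intended exposure.

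It is also fair that no sentence says in words that co-starters are DEX+, and that section V offers further measure definitions on request. The classification follows from the stated rules read together.

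A reader might infer that the co-starters bring uncontrolled severity into the DEX+ arm. The documents do not support that. Shock, ARDS, organ failure, pressors, kidney replacement therapy, ECMO and ICU status through Day T are candidate propensity score covariates, and the modified WHO (mWHO) severity category is a risk-set matching factor. CSI- patients can have all of these. What cannot be matched is the second drug; beyond it there is only the residual confounding that section VIII.A already acknowledges.

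The initial-treatment approach, likened in V.E to intention-to-treat, does not answer the point. It covers treatment changes after index, whereas Day T co-use is part of the exposure at baseline.

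**Conclusion.** The point holds as a one-sided exposure rule on Day T in the primary comparison. As written, the primary hazard ratio is for DEX with or without another CSI at index against no CSI, and its DEX+ arm differs in composition from that of Secondary II. No covariate, censoring rule or planned sensitivity analysis corrects this.

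Its size is unknown. The illustration rests on an assumed share, assumed hazard ratios and a simple weighted average. It shows only that the matter is trivial if co-starters are about 1% of DEX+ and could be noticeable at around 10%. A reader might infer a bias in a known direction, or a larger one in the invasive ventilation subgroup. The protocol gives no figure that supports either.

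A reader might also infer that Secondary II leaves PRED and HC co-starters in. It does not, since section III excludes them; that sentence is simply not repeated in V.C.2. Secondary I has the same unrestricted DEX+ arm, but its referent may include patients newly given a non-DEX CSI, so the asymmetry is sharpest in the primary comparison.

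**What to change.** In V.C.2, under the primary objective, exclude from DEX+ any patient with a record of another systemic CSI (MPRED, PRED or HC) on Day T. Report the number removed, by mWHO category, in the Diagnostic Phase; this needs no outcome data by treatment. Add a sensitivity analysis that retains these patients.

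The reverse is also acceptable: keep them in the primary analysis, state the exposure in sections III and V.B as DEX with or without another CSI at index, and make the exclusion the sensitivity analysis. Either way the classification should be written down before the Inferential Phase.

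Secondary II needs only the section III exclusion of other CSIs carried into its V.C.2 paragraph.

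The cost is one cohort filter on drugs already coded and a loss of DEX+ patients that should be small, though the documents give no count. The filter does not yield a pure DEX-only effect: a CSI added after Day T stays in DEX+ under the initial-treatment approach, and the report should say so.

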### 3. Exclusion criteria

Patients who meet any of the following criteria will be excluded from the study cohort:

- No interaction with the healthcare system (medical encounter) in the 183 days prior to and including hospital admission (*Day -183 to Day 0*) to minimize the potential for misclassification of baseline covariates and/or new use
- No age or sex recorded in the 183 days prior to and including hospital admission (*Day -183 to Day 0*) as required for matching
- No geographic region recorded in 183 days prior to and including hospital admission (*Day -183 to Day 0*) as necessary to adjust for regional variation
- Any recorded use of any CSI (dispensing or remaining supply) in the 90-day washout prior to the treatment index date (*Day T-90 to Day T-1*) to satisfy new use definition
- Any record of a COVID-19 vaccine recorded on or any time prior to the treatment index date given that these patients are assumed to be selectively different (*Day S to Day T*)

The following will be evaluated (one at a time) in sensitivity analyses in order to tighten or loosen some of the exclusion criteria:

- Two sensitivity analyses will restrict the study population by adding the following further exclusions: (1) patients who entered the cohort prior to the release of the initial RECOVERY trial results; and (2) patients who initiated DEX use more than 1 day after the hospital admission date [see section *VII. SENSITIVITY ANALYSES, SA1, SA2*].
- Two sensitivity analyses will broaden the study population by loosening exclusions: (1) extend the lookback period to confirm a prior healthcare encounter to 365 days to allow for better capture of covariates among patients who do not have as frequent medical encounters (office visit or otherwise); and (2) allow patients with confirmed COVID-19 only after treatment index during the index hospitalization (no confirmation on/prior to treatment index or within 21 days prior to admission) [see section *VII. SENSITIVITY ANALYSES, SA3, SA4*].

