## C. Study population

### 1. Cohort entry

#### Hospitalized Patients with COVID-19:

Patients will enter the cohort upon the admission date of the first qualifying inpatient hospitalization observed in the hospital chargemaster data. The first eligible cohort entry date is **01-April-2020**, the date when the ICD-10 code for COVID-19 diagnosis was added. The last possible cohort entry date will be 60 days prior to the last date of available data [see *Appendix A.5 Exploration 5* for additional detail justifying this design decision].

COVID-19 confirmation was defined as either of the following occurring between 21 days prior to the hospital admission date and the treatment index date, which is described in section C.2. below (inclusive; **Day -21 to Day T**):

- Outpatient medical encounter prior to or on the admission date or diagnosis 'present at admission' with ICD-10-CM diagnosis of U07.1 for COVID-19, virus identified; OR
- positive or presumptive positive SARS-CoV-2 diagnostic laboratory test result

The decision to include either diagnosis or positive laboratory test results was based on an initial exploration [see justification detail in *Appendix A.1. Exploration 1*].

For the DEX+ versus MPRED+ comparison (**Secondary Objective II**), given the increased use of MPRED earlier on in the COVID-19 pandemic, we may consider delaying the cohort entry to start in May or June pending data exploration.

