- **COVID-19 diagnosis:** The unique ICD-10 code for COVID-19 diagnosis (U07.1: COVID-19, virus identified) was created by the World Health Organization (WHO) in April 2020. Prior to the widespread use of the new code, other respiratory-related codes were used for billing purposes. We chose to delay the start of our cohort selection to April when the code was available. There is a possibility that early on, some facilities were not yet using the new code. However, given our findings from exploration 1 [see *Appendix A.1. Exploration 1*], concerns about the specificity of the ICD-10 codes other than the designated U07.1 code, we agreed to proceed with the definition of confirmed COVID-19 via diagnosis of U07.1 or positive/presumptive positive SARS-CoV-2 diagnostic laboratory test result.
- **Unstructured laboratory encounter data:** In addition to using the unique diagnosis code for COVID-19 (ICD-10: U07.1), we will include patients without a diagnosis claim if they have laboratory results identifying positive or presumed positive SARS-CoV-2 diagnostic test via nucleic acid amplification test (NAAT). The laboratory data has unstructured free-text for test type and results, which present a challenge. Although we anticipate that we will not be able to categorize all COVID-19 laboratory results, we rely on an algorithm developed by the data vendor to discern the majority of test types and results.

- **Open claims:** Data from open claims can be captured within days of a healthcare encounter to provide near-real-time data. However, the composition and completeness may be less stable for the most recent calendar dates. Based on our findings from exploration 5, we have truncated cohort entry to remove the last 60 days, which should minimize this concern [see *Appendix A.5 Exploration 5*].
- **Lack of enrollment information in open claims to determine denominator of patients at risk with the same potential to contribute baseline data:** Without beneficiary enrollment information like that included with closed claims data, use of “open” datasets limits the ability to clearly determine when a patient is observable or “at risk.” However, we are confident that our cohort will include all patients hospitalized available in the data and will additionally require the presence of any encounter during the 183-day baseline period for inclusion as a proxy for enrollment and extend this period to 365 days in a sensitivity analysis.

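### The no-encounter exclusion in section V.C.3 counts the admission day, so the index stay itself satisfies it; Figure 2 ends the same window on Day -1

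*Protocol*

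**What the plan says.** Four places in the protocol bear on this rule.

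- **Section V.C.3, first exclusion bullet:** "No interaction with the healthcare system (medical encounter) in the 183 days prior to and including hospital admission", with the window printed as Day -183 to Day 0. The stated reason is "to minimize the potential for misclassification of baseline covariates and/or new use".
- **Section V.A, Figure 2, baseline exclusion:** "Exclude patients without activity in the 183 day baseline period (Day -183 to Day -1".
- **Section VIII.A, on the lack of enrollment information in open claims:** the study "will additionally require the presence of any encounter during the 183-day baseline period for inclusion as a proxy for enrollment". No day range is printed there.
- **SA3, in section V.C.3, Table 5 and Appendix B:** V.C.3 introduces it with "Two sensitivity analyses will broaden the study population by loosening exclusions" and says that it will "extend the lookback period to confirm a prior healthcare encounter to 365 days". Table 5 gives its purpose as bringing in people who have no encounter within 183 days but have one within 365 days before admission.

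Section V.C.1 fixes what Day 0 is: "Patients will enter the cohort upon the admission date of the first qualifying inpatient hospitalization observed in the hospital chargemaster data".

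**The concern.** An observability requirement is useful only if a patient can fail it. V.C.3 lets the admission day count, and the admission is itself the event that brings the patient into the cohort. The requirement then says nothing about whether the patient could be seen in the data before admission.

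That matters because of what the rule is for. Table 3 measures baseline comorbidities, co-medications and utilization on Day -183 to Day -1, and Table 2 matches on a comorbidity score over the 183-day baseline period. A patient with no record in that period has those conditions coded as absent, whether or not they are. Risk-set and propensity-score matching work on recorded values, so they can balance sparse records between arms but cannot restore missing history. The open claims carry no enrollment dates, and section VIII.A relies on this rule as the substitute.

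The rule also decides who is in the primary cohort. Two programmers, one working from V.C.3 and one from Figure 2, would build different cohorts.

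**Working it through.** No sample-size or power figure is involved. The check compares the two windows and asks whether the index admission alone meets each of them.

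**Inputs**

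| Item | Value | Source |
|---|---|---|
| Encounter window, text | Day -183 to Day 0 | V.C.3 |
| Encounter window, figure | Day -183 to Day -1 | V.A, Figure 2 |
| Event on Day 0 | Index inpatient admission, for every cohort member | V.C.1 |
| Baseline covariate window | Day -183 to Day -1 | V.F, Table 3 |
| SA3 lookback | 365 days before admission | V.C.3; VII, Table 5 |

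**Step 1: window lengths, counted inclusively**

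- V.C.3: 0 - (-183) + 1 = 184 days.
- Figure 2: -1 - (-183) + 1 = 183 days, which agrees with the figure's own description of a 183-day period.
- The extra day in V.C.3 is the admission day.

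**Step 2: who is excluded**

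Let E be the set of days on which a patient has an encounter. Cohort entry requires that Day 0 is in E.

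- V.C.3 excludes a patient if E has no day in [-183, 0]. Day 0 is always in E, so no patient qualifies for exclusion: **0 excluded**.
- Figure 2 excludes a patient if E has no day in [-183, -1]. This can happen, so the rule has content.

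**Step 3: what SA3 adds through this criterion**

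- Under literal V.C.3, the primary analysis has already admitted everyone that the encounter rule could exclude. Widening the window to [-365, 0] adds **0 patients**.
- Under Figure 2, SA3 adds patients with no encounter in [-183, -1] and at least one in [-365, -184]. That band is 365 - 183 = 182 days long.
- SA3 also re-measures covariates over 365 days. That part does not depend on the encounter rule and is unaffected.

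**Step 4: does a charitable reading of V.C.3 remove the conflict?**

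Suppose the index stay is silently set aside but other Day 0 records count. Table 3 lists emergency room and ambulance encounters among the admission-day covariates. A patient whose only other record is a same-day emergency visit would pass V.C.3 and fail Figure 2. The two windows still disagree, which is why the correction should cover any Day 0 record and not only the index stay.

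**The case against.** The strongest reply is that the protocol already shows what was meant. Figure 2 and Table 3 end the baseline on Day -1, section VIII.A describes an enrollment proxy, and the later SA3 bullet in V.C.3 speaks of a prior encounter. The adjacent age, sex and region bullets use Day -183 to Day 0, where including the admission day is sensible, so the encounter bullet may simply have picked up the same wording. This stands: the intent is recoverable, and nothing shows that the cohort would be built on the zero-exclusion reading. It lowers the seriousness. It does not make the written rule correct, because V.C.3 is the formal list of exclusions and disagrees with the figure on a printed day.

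Three stronger readings are tempting and are not supported.

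- **That the protocol uses competing definitions of the qualifying event.** The wording varies, but the SA3 text uses *medical encounter* and *healthcare encounter* interchangeably, and *any encounter* in VIII.A is ordinary shorthand. Only *activity* in Figure 2 could be broader, and nothing says that it is. Whether a pharmacy or laboratory record alone would qualify is operational detail; section V says that further measure definitions are available on request.
- **That section VIII.A prints a conflicting window.** It prints none. It relies on the 183-day baseline period, which ends on Day -1 only by reference to Figure 2 and Table 3, so that conflict arises by consequence.
- **That the hazard ratio is biased in a known direction.** The protocol gives no count of patients without a pre-admission encounter and no split by treatment, so neither the size nor the direction of any bias can be derived.

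**Conclusion.** The point holds as one explicit mismatch, Day 0 in V.C.3 against Day -1 in Figure 2, with two consequences. As written, the V.C.3 rule excludes 0 patients and so cannot serve as the enrollment proxy. SA3's population-broadening part then adds 0 patients through this criterion.

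The conclusion rests on two things: that the index inpatient stay is an interaction with the healthcare system in the ordinary sense, and that the protocol nowhere sets it aside. The number of patients who would move between the two versions cannot be computed from the document.

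This should be fixed before the cohort is built, because it is a primary eligibility rule. It is not a fatal flaw, since the rest of the protocol points to a pre-admission window.

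**What to change.** 1. In V.C.3, change the encounter window to Day -183 to Day -1, and state that neither the index admission nor any other Day 0 record counts.
2. State the matching SA3 encounter window as Day -365 to Day -1 in V.C.3 and Table 5. Table 5 already describes the encounter as falling before admission, so this only makes the days explicit.
3. Optionally, use one term for the qualifying event in V.C.3 and Figure 2 (*medical encounter* or *activity*). This is editorial alignment, not the correction of a separate error.

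The cost is a few one-line edits and no new data. The downside is a somewhat smaller primary cohort than the literal V.C.3 wording would give. If that affects the sample-size item in Table 4, section IV already provides for further data updates until the requirement is met.
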